7.1 Overall Study Design and Plan: Description

This is a multicenter, randomized, double-blind, parallel-group study designed to assess the safety, efficacy and tolerability of IDP-121 Lotion in comparison with its vehicle. To be eligible for the study, subjects must be at least 9 years of age and older and have a clinical diagnosis of moderate to severe acne vulgaris (a score of 3 or 4 [moderate to severe] on the EGSS scale).

Approximately 800 subjects will be enrolled into this study and randomized into one (1) of two (2) treatment groups: 400 subjects in the IDP-121 Lotion, once daily application group,

and 400 subjects in the IDP-121 Lotion Vehicle, once daily application group. Subjects will be enrolled at a minimum of 32 and maximum of 50 independent study centers. The duration of treatment will be 12 weeks. Subjects will be evaluated at Screening, Baseline and at subsequent follow-up visits (Weeks 4, 8, and 12).

An interactive web based response system (IWRS) will be employed to facilitate randomization of study patients. Treatment assignments and study drug kit numbers will be generated centrally by the IWR system. At each clinical site, subject numbers will be assigned consecutively at the screening visit starting with 001.

The assigned study drug will be applied topically to the face once daily for 12 weeks. The initial application will be made at the investigational center as per instruction from the study coordinator or designee. The subjects will be instructed to avoid exposure to direct sunlight to prevent sunburn. Subjects will apply their daily treatments at home as explained by the study coordinator or designee at each investigational center. During post-baseline study visits (Weeks 4, 8 and 12) the subjects will be asked to return their used tubes of study drug and will be dispensed new tubes of study drug (only Weeks 4 and 8; Week 12 will be final visit). During the study, each subject will only be permitted to use approved non-medicated cleansers, moisturizers and sunscreens.

Subjects will be asked to complete three questionnaires during the study: the Subject Self Assessment scale (SSA, Appendix 17.3), the Patient Satisfaction Survey (PSS, Appendix 17.4) and the Acne-Specific Quality of Life Questionnaire (Acne-QoL, Appendix 17.5). The Investigator assessments (EGSS, lesion counts) will be conducted independently of these subject self assessments. The EGSS should be completed prior to the lesion counts. Subjects will assess the severity of their acne at the baseline visit and at Weeks 2 (at home), 4, 8, and 12 by completing the SSA. The Week 2 SSA form will be dispensed to the subject at the baseline visit with instructions to complete it two weeks later and return it the Week 4 visit; sites should call the Subject at Week 2 to remind them to complete the SSA. Subjects will complete the PSS related to prior therapy at baseline, and at Week 12 will complete the PSS related to current study medication. The Acne-QoL will be completed at baseline and Week 12. Inferential statistical analysis will not be performed on these questionnaires; the subjective responses will be compared between treatment groups for trends.

Information on reported and observed adverse events (AEs) will be obtained at each visit. An abbreviated physical examination will be performed at Baseline and Week 12 (end of treatment, final visit) for all subjects.

For all female subjects of childbearing potential, urine pregnancy testing will be performed at Screening and confirmed at Baseline with a urine pregnancy test prior to randomization, and at Weeks 4, 8 and 12. Serum pregnancy tests will also be conducted at Screening and Week 12.

Subjects who terminate study participation early will be asked to complete all Week 12 assessments, as appropriate. Subjects who discontinue from the study during the treatment period will not be replaced.

Table 1. Study Design and Schedule of Assessments

PROCEDURES	VISIT 1 ¹ Screening Visit	VISIT 2 ² Baseline Day 0	VISIT 3 ² Week 4 (Day 28 ±3 days)	VISIT 4 ² Week 8 (Day 56 ± 3 days)	VISIT 5 ^{2,3} Week 12 (Day 84 -3/+5 days)
Informed consent/Accent	X				
Obtain Subject Number from IWRS	X				
Demographics	X				
Medical history	X	X			
Inclusion/Exclusion criteria	X	X			
Previous therapies	X				
PSS & Acne-QoL		X			X
SSA ⁴		X	X	X	X
Urine Pregnancy Test (UPT) (FOCBP)	X	X	X	X	X
Serum Pregnancy Test (FOCBP)	X				X
Abbreviated physical examination		X			X
Oily/shiny skin assessment		X			X
Lesion Counts	X	X	X	X	X
EGSS	X	X	X	X	X
Photographs (select sites only)		X			X
Cutaneous Safety Evaluation		X	X	X	X
Tolerability Evaluation		X	X	X	X
Randomization in IWRS (obtain kit #)		X	X	X	
Administer Subject Instructions (Appendix 17.1)		X			
Dispense Study Drug ⁵		X	X	X	
Weigh Study Drug		X	X	X	X
Study Drug applied at investigational center		X			
Study Drug Collected			X	X	X
Subject Diary Calendar dispensed		X	X	X	
Subject Compliance Reviewed / Diary			X	X	X
Adverse Events	X	X	X	X	X
Concomitant Therapy and Prohibited Therapies Review	X	X	X	X	X
End of Study					X

¹ If no washout is needed, Visits 1 and 2 may occur on the same day. If a washout is needed, Visit 2 must occur after the appropriate washout period.

² All visit dates are in reference to baseline, e.g., Visit 4 occurs 8 weeks +/- 3 days after baseline visit.

³ All Week 12 procedures should be completed for all subjects who terminate early.

⁴ The Week 2 SSA will be sent home with the subject during the baseline visit (Visit 2) with instructions to complete it at two weeks and return it at the Week 4 visit. The site should call the subject at Week 2 to remind them to take the Week 2 SSA.

⁵ Dispense one tube of test material at the Baseline, Week 4 and Week 8 visits.

8 Selection and Withdrawal of Subjects

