Subjects will be asked to complete three questionnaires during the study: the Subject Self Assessment scale (SSA, Appendix 17.3), the Patient Satisfaction Survey (PSS, Appendix 17.4) and the Acne-Specific Quality of Life Questionnaire (Acne-QoL, Appendix 17.5). The Investigator assessments (EGSS, lesion counts) will be conducted independently of these subject self assessments. The EGSS should be completed prior to the lesion counts. Subjects will assess the severity of their acne at the baseline visit and at Weeks 2 (at home), 4, 8, and 12 by completing the SSA. The Week 2 SSA form will be dispensed to the subject at the baseline visit with instructions to complete it two weeks later and return it the Week 4 visit; sites should call the Subject at Week 2 to remind them to complete the SSA. Subjects will complete the PSS related to prior therapy at baseline, and at Week 12 will complete the PSS related to current study medication. The Acne-QoL will be completed at baseline and Week 12. Inferential statistical analysis will not be performed on these questionnaires; the subjective responses will be compared between treatment groups for trends.

Information on reported and observed adverse events (AEs) will be obtained at each visit. An abbreviated physical examination and safety labs will be performed at Baseline and Week 12 (end of treatment, final visit) for all subjects.

For all female subjects of childbearing potential, urine pregnancy testing will be performed at Screening and confirmed at Baseline with a urine pregnancy test prior to randomization, and at Weeks 4, 8 and 12.

Subjects who terminate study participation early will be asked to complete all Week 12 assessments, as appropriate. Subjects who discontinue from the study during the treatment period will not be replaced.

Table 1. Study Design and Schedule of Assessments

PROCEDURES	VISIT 1 ¹ Screening Visit	VISIT 2 ² Baseline Day 0	VISIT 3 ² Week 4 (Day 28 ±3 days)	VISIT 4 ² Week 8 (Day 56 ± 3 days)	VISIT 5 ^{2,3} Week 12 (Day 84 -3/+5 days)
Informed consent/Assent	X				
Obtain Subject Number from IWRS	X				
Demographics	X				
Medical history	X	X			
Inclusion/Exclusion criteria	X	X			
Previous therapies	X				
PSS & Acne-QoL		X			X
SSA ⁴		X	X	X	X
Urine Pregnancy Test (UPT) (FOCBP)	X	X	X	X	X
Abbreviated physical examination and vital signs		X			X
Safety labs (hematology, CBC/diff, urinalysis)		X			X
Oily/shiny skin assessment		X			X
Lesion Counts	X	X	X	X	X
EGSS	X	X	X	X	X

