Photographs (select sites only)		X			X
Cutaneous Safety Evaluation		X	X	X	X
Tolerability Evaluation		X	X	X	X
Randomization in IWRS (obtain kit #)		X	X	X	
Administer Subject Instructions (Appendix 17.1)		X			
Dispense Study Drug ⁵		X	X	X	
Weigh Study Drug to the nearest 0.1gram		X	X	X	X
Study Drug applied at investigational center		X			
Study Drug Collected			X	X	X
Subject Diary Calendar dispensed		X	X	X	
Subject Compliance Reviewed / Diary			X	X	X
Adverse Events	X	X	X	X	X
Concomitant Therapy and Prohibited Therapies Review	X	X	X	X	X
End of Study					X

¹ If no washout is needed, Visits 1 and 2 may occur on the same day. If a washout is needed, Visit 2 must occur after the appropriate washout period.

² All visit dates are in reference to baseline, e.g., Visit 4 occurs 8 weeks +/- 3 days after baseline visit.

³ All Week 12 procedures should be completed for all subjects who terminate early.

⁴ The Week 2 SSA will be sent home with the subject during the baseline visit (Visit 2) with instructions to complete it at two weeks and return it at the Week 4 visit. The site should call the subject at Week 2 to remind them to take the Week 2 SSA.

⁵ Dispense one tube of test material at the Baseline, Week 4 and Week 8 visits.

8 Selection and Withdrawal of Subjects

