8.3 Subject Withdrawal Criteria

Reasons for withdrawal may include, but are not limited to, the following:

- Acne flare, as determined by the investigator, which requires treatment with a disallowed therapy.
- Either at the investigator's request, for tolerability reasons (eg, severe adverse reactions), or at the subject's request.
- When the requirements of the protocol are not followed.
- When a concomitant therapy likely to interfere with the results of the study is reported, or required by the subject (the investigators will report all such information

on the source documents/case report forms (CRFs) and decide, in accordance with the sponsor, whether the subject is to be withdrawn).

- When a subject is lost to follow-up. The investigators will try twice to reach the subject by telephone and will send a follow-up letter by certified mail before considering that the subject is lost to follow-up. These actions will be reported on the End of Study CRF and a copy of the follow-up letter maintained in the investigator's file.

All premature discontinuations and their reasons must be carefully documented by the investigator on the final CRF, and, if need be, on the AE form. In any case, no subject who has been included and has a study number assigned can be replaced by another if they discontinue prematurely for whatever reason. All data gathered on the subject prior to termination will be made available to the sponsor.

Reasons for study completion/discontinuation as listed on the final report form are defined as follows:

Normal Study Completion – Subject completes the study as planned in the protocol.

Adverse Event – Complete AE form.

Death – Complete SAE form.

Subject Request – Consent withdrawal, subject moved, schedule conflicts.

Protocol Violation – Contact the Sponsor or designee before making decision.

Lost to Follow-Up – Document with 2 phone calls and a certified letter.

Pregnancy – Subject will discontinue study drug immediately, but will be followed to term. Complete pregnancy and SAE forms.

Worsening Condition – Subject requires alternate treatment for acne before the end of the study and the investigator determines it is not due to lack of efficacy.

Lack of Efficacy – Subject requires alternate treatment for acne after at least 2 weeks of study drug treatment and the risk of continuing the subject in the study outweighs the benefit as determined by the investigator.

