12. The study coordinator or designee will instruct the subject on the proper application procedure for the study drug per Section 10.1.3, and will provide written subject use instructions to the subject (Appendix 17.1). For the first application, the subject will apply the study drug at the investigational center under the direction of the study coordinator or designee. The study drug should be applied after all clinical assessments. The study coordinator or designee will instruct the subjects to apply the study drug once daily at home.
13. Record any AEs or changes in AEs since the screening visit and/or reported spontaneously by the subject.
14. *Selected Sites only* - Obtain representative photographs of the face.
15. Schedule the next study visit at Week 4 (Day 28 ± 3 days). Remind the subject to not apply test medication on day of next study visit, prior to the clinic visit.

11.1.3 Visit 3 and 4: Week 4 (Day 28 ± 3 Days) and Week 8 (Day 56 ± 3 Days) Visits

The following procedures will be conducted at this visit (if a subject terminates early, all final visit (Week 12/Final Visit) procedures must be performed):

1. The take-home Week 2 SSA will be collected during the Week 4 study visit.
2. The Week 4 or Week 8 SSA will be conducted and collected.
3. The Evaluator will perform the efficacy evaluations including the Evaluator's Global Severity Score (EGSS), inflammatory lesion counts and non-inflammatory lesion counts. The EGSS is performed prior to the lesion counting. Every effort should be made for the same qualified and validated evaluator to perform the efficacy evaluations at all visits from Baseline to Week 12 for the same subject.
4. The Evaluator will perform Cutaneous Safety and Tolerability Evaluations.
5. Record changes in any concomitant medications since the previous visit under Prior and Concomitant Medications or Therapies. Check for prior and concomitant therapies as per Section 9.4.
6. Record any new AEs reported spontaneously by the subject or changes in any ongoing AEs.

7. Perform a Urine Pregnancy Test for all females that are pre-menses and females of childbearing potential. The urine pregnancy tests will be supplied by the CRO.

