11.3 Evaluation of Safety

Safety assessments will be conducted at baseline and each subsequent visit.

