11.4.2 Documenting Adverse Experiences

It is the responsibility of the investigator to document all AEs that occur during the course of the study. The AEs should be documented as a single medical diagnosis. When this is not possible, the AE should be documented in terms of signs and/or symptoms observed by the investigator or reported by the subject at each study visit. Each AE which appears to be independent of any prior event will be reported separately.

All AEs occurring after the subject signs the informed consent through the last study visit must be reported, regardless of whether or not the AEs are considered drug-related. All AEs, whether in response to a query, observed by the study site personnel, or reported spontaneously by the subject, will be recorded. Any AEs deemed related to treatment reported or observed at the final study/treatment visit will be followed until stabilization or resolution (or up to 30 days after final study visit).

At each visit during the study, the subject will be assessed for the occurrence of new and ongoing AEs. Cutaneous tolerability signs and symptoms that result in the subject's requiring a concomitant therapy or discontinuation from the study will be reported as an AE. The following data will be collected on all AEs and recorded on the appropriate CRF:

- Event name (diagnosis preferred, if unknown, record the signs/symptoms)
- Onset date and end date
- Maximum intensity (severity)
- Seriousness
- Action taken regarding study drug
- Corrective treatment, if given

- Outcome

In addition, the investigator's assessment of causality will be recorded.

Vital sign abnormalities are to be recorded as AEs only if they are clinically significant (for example: are symptomatic, requiring corrective treatment, leading to discontinuation or fulfilling a seriousness criterion).

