12.8 Additional Statistical Considerations

12.8.1 Analysis Populations

Approximately 800 subjects at least 9 years of age and older with moderate or severe acne (a score of 3 or 4 [moderate to severe] on the EGSS scale) will be enrolled and randomized in the study. With a 1:1 randomization ratio, it is anticipated that:

- 400 subjects will be randomized to receive IDP-121 Lotion, once daily application
- 400 subjects will be randomized to receive IDP-121 Vehicle Lotion, once daily application

The ITT population will consist of all randomized subjects who received study medication. The safety population will be comprised of all randomized subjects who are presumed to have used the study medication at least once and who provide at least one post-baseline evaluation.

An intent-to-treat (ITT) analysis will be conducted on all study subjects. A per-protocol (PP) analysis will also be conducted. Subjects will be eligible for the PP analysis if they complete the 12-week evaluation without noteworthy study protocol violations (i.e., any subject or investigator activity that could have possibly interfered with the therapeutic administration of the treatment or the precise evaluation of treatment efficacy). The PP population will include subjects in the safety population who do not meet any of the following criteria:

- Failed any of the inclusion/exclusion criteria;
- Have taken any interfering concomitant medications;
- Did not attend the Week 12 visit, with the exception of a discontinuation from the study due to an adverse event related to study treatment or documented lack of treatment effect;
- Missed both the week 4 and week 8 visits;
- Have not been compliant with the dosing regimen (i.e. Subjects may not miss more than five consecutive days of dosing and must take 80-120% of expected doses. The number of expected doses will be determined for each subject based on the length of their participation in the study);
- Out of visit window at the 12-week visit.

Prior to breaking the blind, other additional criteria may be added to the list to accommodate for unforeseen events that occurred during the conduct of the trial that result in noteworthy study protocol violations.

The safety population will be comprised of all randomized subjects who are presumed to have used the study medication at least once and who provide at least one post-baseline evaluation.

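### The Week 2 reminder call carries no safety question, so a treated subject who stops early and does not return has no scheduled post-baseline safety assessment and falls outside the safety population

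*Combined protocol and SAP*

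**What the plan says.** Section references are to Amendment 3. The wording on the call is the same in both protocol versions in the file.

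- **The call.** Section 7.1: "sites should call the Subject at Week 2 to remind them to complete the SSA". Table 1, footnote 4: "The site should call the subject at Week 2 to remind them to take the Week 2 SSA". Neither place mentions AEs, tolerability or drug use. Table 1 has no Week 2 column. The Week 2 Subject Self Assessment (SSA) form is handed in at the Week 4 visit.
- **When safety is asked about.** Section 7.1: "Information on reported and observed adverse events (AEs) will be obtained at each visit". Section 11.3: "Safety assessments will be conducted at baseline and each subsequent visit". The first visit after Baseline is Week 4.
- **Who is in the safety population.** Section 12.8.1: randomized subjects "presumed to have used the study medication at least once and who provide at least one post-baseline evaluation". The ITT population in the same section needs only randomization and receipt of study medication.
- **Other routes to a record.** Section 11.4.2: "All AEs, whether in response to a query, observed by the study site personnel, or reported spontaneously by the subject, will be recorded". Section 8.3: "All premature discontinuations and their reasons must be carefully documented by the investigator on the final CRF, and, if need be, on the AE form". Section 8.3 also asks for two telephone calls and a certified letter before a subject is declared lost. Section 11.1.3 and Table 1, footnote 3, call for the Week 12 procedures in subjects who terminate early.

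**The concern.** Safety and tolerability are part of the study objective, and entry starts at age 9. The Introduction names erythema, dryness, peeling, scaling and irritation as effects that may limit topical tretinoin. Section 11.3.1 makes tolerability signs that lead to interruption or discontinuation reportable as AEs. A contact two weeks into treatment is well placed to pick up such events. The plan provides that contact but asks nothing about safety.

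As planned, the first four weeks on drug are described systematically only in subjects who attend a later visit. Early intolerance that ends in loss of contact can go unrecorded. Even when it is recorded, the subject may not be counted in the safety tables.

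**Working it through.** **Step 1: length of the interval.** The Week 4 visit is Day 28 ± 3 days (Section 11.1.3). 28 − 3 = 25 and 28 + 3 = 31, so the first scheduled safety question after Day 0 falls on Day 25 to 31. A question on the Week 2 call would come at about Day 14.

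**Step 2: follow one subject.** The subject is randomized, makes the first application at the site on Day 0, stops in the second week and does not attend again.

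- *ITT:* included, because study medication was received. Missing Week 12 efficacy values are imputed under Section 12.1.8.
- *Safety population:* use is established on Day 0, but there is no post-baseline evaluation, so the subject is excluded. The protocol does not say whether a telephone contact counts as an evaluation.
- *Scheduled AE query or tolerability score after Baseline:* none.
- *Week 2 SSA:* not returned, because it is collected at Week 4. It asks about acne severity, so it would carry no safety content in any case.

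**Step 3: what each other route needs.**

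- Early-termination procedures need the subject to come back. Section 11.1.3 words them as mandatory, Table 1 footnote 3 as expected, and Section 8.3 as a request where possible.
- Lost-to-follow-up calls need an answer, and no AE question is prescribed for them.
- The discontinuation reason goes on the final CRF, but the AE form is conditional. A reason such as subject request or loss to follow-up says nothing about tolerability.
- A spontaneous report needs the subject to volunteer it. The by-subject AE listing in Section 12.2.1 is not stated to be restricted to the safety population, so a volunteered AE could appear there.

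**Step 4: subjects who do return.** Week 4 covers the interval in retrospect, but Section 11.3.1 rates itching, burning and stinging as they are at the visit, while Section 11.3.2 rates them as an average since the previous visit. The first misses symptoms that have resolved; the second averages about four weeks of recall. The two sections must be reconciled.

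**Step 5: possible size.** The documents give no rate of loss before Week 4, so everything here beyond the 400 per arm is assumed. I also take the AE tables to use the safety population, which Section 12.2 does not state outright. Let a fraction d of 400 never return. Then 400 × d subjects leave the safety population. For illustration, suppose 40 of the remaining subjects in the arm have an AE and a share s of the non-returners had one that was not tabulated.

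Tabulated rate = 40 / (400 − 400d). All-treated rate = (40 + 400ds) / 400.

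| d | Lost per arm | Safety n | Tabulated | All treated, s = 10% | s = 50% | s = 100% |
|---|---|---|---|---|---|---|
| 1% | 4 | 396 | 10.1% | 10.1% | 10.5% | 11.0% |
| 2% | 8 | 392 | 10.2% | 10.2% | 11.0% | 12.0% |
| 5% | 20 | 380 | 10.5% | 10.5% | 12.5% | 15.0% |
| 10% | 40 | 360 | 11.1% | 11.0% | 15.0% | 20.0% |

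If non-returners have AEs about as often as everyone else (s = 10%), the understatement all but vanishes. It grows only if AEs are over-represented among them: about 2 percentage points at d = 5% and s = 50% (12.5% − 10.5%).

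**The case against.** The strongest reply is that this is a design choice with several safeguards. Nothing in the schedule is contradictory, a first visit at four weeks is workable, and no primary or secondary efficacy analysis is affected. Irritation mentioned on the Week 2 call would already have to be recorded as a spontaneous report. A baseline-issued diary records missed applications. All of this stands, and it keeps the point minor.

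The reply also limits what the remedy can do. A call cannot reach subjects who do not answer, and it misses those who stop after about Day 14. The counts in the table are therefore a ceiling on what could be recovered. The exclusion itself comes from the population definition and could be repaired without changing the call.

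Four stronger readings are tempting, and the documents do not support them:

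- *Early stoppers leave no safety record.* The routes in Step 3 can produce one. What is missing is a scheduled query and score, and a place in the safety population.
- *Every subject is phoned about an efficacy form.* The call is something sites should do, with no stated documentation. The SSA is exploratory, is not a primary, secondary or supportive endpoint, and is summarized under Assessment of Safety.
- *A few losses would decide which AE terms are tested, because the plan's 1% threshold is 4 of 400.* That threshold counts subjects reporting the same class or term. Losses for any reason are a different count.
- *Losses will be heavier on active drug.* The Introduction describes side effects, not early dropout, so this is inference.

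One item cannot be checked: the Subject Instruction Sheet (Appendix 17.1) is not in the reviewed text and may tell subjects to call about side effects.

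**Conclusion.** The point holds as a low-cost improvement, not as an error. The plan has one contact between Day 0 and Day 25 to 31, and its only stated purpose is a questionnaire reminder. A treated subject who stops early and does not return has no scheduled post-baseline safety assessment and is counted for efficacy but not for safety. The existing safeguards reduce the gap without closing it, because each depends on the subject's cooperation.

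Its size is unknown. The range of 4 to 40 subjects per arm rests on an assumed early loss of 1% to 10%, and any understatement of AE rates further requires that non-returners had more AEs than those who stayed.

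**What to change.** 1. In Section 7.1 and Table 1, footnote 4, have the Week 2 call also ask the standard AE question and whether study drug has been interrupted or stopped. Record the answers on the AE and dosing CRF pages.
2. In Section 12.8.1, and in the matching Synopsis text, either state that this contact counts as a post-baseline evaluation for safety, or define the safety population as everyone randomized who is presumed to have applied study drug at all. The second option also covers subjects the call does not reach.

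The SSA answer should not be taken by telephone, because that would change the mode of a self-completed form at one time point.

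The cost is a few minutes per call, one CRF page and protocol wording, with no added visit or call. The recorded AE rate may rise slightly, and some subjects in the safety population will have no tolerability scores, so those tables should show the number assessed at each visit. The change concerns data collection and population definition only; sample size and power are unaffected.
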